## 6. STUDY PRODUCT

### 6.1. Study Product Description

#### 6.1.1. Lidoderm® Patch 5%

Lidoderm® patch 5% is a prescription product that delivers approximately  $3 \pm 2\%$  of the applied dose over a 12 hour wear time. At least 95% (665 mg) of lidocaine is expected to remain in the worn patch after removal.

#### 6.1.2. Lidocaine HCl Injection, 20 mg/1 ml Preservative Free Single Dose Vials

Lidocaine hydrochloride injection is a prescription product that can be used for a variety of indications, including local anesthesia and treatment of ventricular arrhythmias.

#### 6.1.3. Lidocaine Patch 5% (Mylan)

The Mylan lidocaine patch 5% is a prescription product that delivers approximately  $11 \pm 4\%$  of the applied dose over a 12 hour wear time. At least 82% (115 mg) of lidocaine is expected to remain in the worn patch after removal.

## 6.2. Acquisition

[figure not shown]
All drug products will be acquired through direct purchase by the Investigational Drug Services (IDS) pharmacy at UIHC.

Department of Pharmaceutical Care  
Investigational Drug Services  
University of Iowa Hospitals and Clinics  
[name]  
[name]  
[name]  
[contact]

## 6.3. Formulation, Packaging, and Labeling

[figure not shown]
#### 6.3.1. Lidoderm® Patch 5%

[figure not shown]
Active ingredient: lidocaine, 700 mg (50 mg per gram of adhesive). In addition to the active ingredient (lidocaine), the following inactive ingredients are present in the patch: dihydroxyaluminum aminoacetate, disodium edetate, gelatin, glycerin, kaolin, methylparaben, polyacrylic acid, polyvinyl alcohol, propylene glycol, propylparaben, sodium carboxymethylcellulose, sodium polyacrylate, D-sorbitol, tartaric acid, and urea. This is a hydrogel patch manufactured by Endo Pharmaceuticals.

### 6.3.2. Lidocaine HCl Injection, 20 mg/1 ml Preservative Free Single Dose Vials

[figure not shown]
Active ingredient: lidocaine hydrochloride. Inactive ingredients: sodium chloride, sodium hydroxide, hydrochloric acid, and water. This injectable is manufactured by Auromedics Pharma LLC.

### 6.3.3. Lidocaine Patch 5% (Mylan)

Active ingredient: lidocaine, 140 mg (50 mg per gram of adhesive). The patch contains a polyisobutylene adhesive matrix. This is a matrix type patch manufactured by Mylan Pharmaceuticals.

### 6.4. Product Stability

Lidoderm® should be stored between 15-30°C (59-86 °F). The Mylan lidocaine 5% patch should be stored between 20-25°C (68-77°F). Lidocaine HCl injection should be stored at 15°-30°C (59°-86°F).

## **6.5. Dosage, Preparation and Administration of Study Product**

### **6.5.1. Application of the Patch**

The application site will be the skin of the mid to lower back. The subject's skin in the area of patch application will be healthy, clean, dry and relatively free of hair before patch application. Hair may be clipped (but not shaved) at the application site prior to patch application dosing, if necessary. A study team member will cleanse the site with water and carefully dry the skin prior to patch application. The patches will be applied to the skin and held firmly in place for 15 – 20 seconds after application. During the 12 hour patch wear time, the subjects will be asked to sit/lay quietly for the majority of their time, so as not to affect patch adhesion.

### **6.5.2. Administration of the IV Injection of Lidocaine Hydrochloride**

A catheter will be inserted into the subject's arm, contralateral to the arm of the IV catheter that will be used for blood sampling. The site of the insertion for the catheter to administer lidocaine hydrochloride will be either near the elbow or the wrist depending on the identification of the vein in the subject. The IV will be injected over 5 minutes using an Alaris Guardrails pump with syringe pump cassette.

## **6.6. Accountability Procedures for the Study Product(s)**

All drug products will be acquired through the University of Iowa IDS pharmacy. The products will be stored in the IDS pharmacy at the conditions noted in the package inserts. The IDS pharmacy will dispense the drug product to a study team member on the morning of, or the business day immediately before, a subject starts a new study arm. If the product is dispensed on the business day before a study, then it will be stored in a locked cabinet in the locked medication room in the CRU. Authorized badge access is required to access the medication room.

Department of Pharmaceutical Care  
Investigational Drug Services  
University of Iowa Hospitals and Clinics  
[name]  
[name]  
[name]  
[contact]

Prior to dispensing the patch, the lot number on both the patch pouch and the product box will be recorded. Prior to dispensing the IV injection, the lot number of the product will be recorded. After removal, the used patches will be stored in sealable foil pouches labeled with subject ID number and shipped to Long Island University.

[name]  
Lachman Institute for Pharmaceutical Analysis  
Long Island University – Brooklyn Campus  
[name]  
[name]

### **6.7. Assessment of Subject Compliance with Study Product**

Subjects will be directly observed at the time of patch application or IV administration by a member of the clinical research team. Administration will be documented on the clinical notes.

### **6.8. Patch System Adhesion Evaluation**

Patch adhesion (for each patch being worn) will be evaluated and scored by study site personnel. The recommended scoring system for adhesion of patches will be adopted as described in the FDA draft Guidance included in **Appendix D**.

- 0 =  $\geq$  90% adhered (essentially no lift off the skin)
- 1 =  $\geq$  75% to  $<$  90% adhered (some edges only lifting off the skin)
- 2 =  $\geq$  50% to  $<$  75% adhered (less than half of the patch lifting off the skin)
- 3 =  $>$  0% to  $<$  50% adhered but not detached (more than half of the patch lifting off the skin without falling off)
- 4 = 0% adhered - patch detached (patch completely off the skin)

### **6.9. Concomitant Medications/Treatments**

Any concomitant medication deemed necessary for the welfare of the subject during any arm of the study may be given at the discretion of the MAI. It is the responsibility of the PI to ensure that details regarding the medication are recorded in full in the subject's data collection forms, along with the routine documentation of any changes in concomitant medication that may have occurred during the study. Within four weeks prior to enrollment, use of medications or treatments that would significantly influence or exaggerate responses to the test product or that would alter inflammatory or immune response to the product or agents deemed to be immunosuppressive as determined by physician investigator is prohibited.

## 7. STUDY SCHEDULE

Study schedule is summarized in **Appendix A**.

### 7.1. Screening 0 to 30 Days

This study will be advertised through the UI campus-wide email system and through the University of Iowa Health Care “Noon News”, a daily announcement flier printed for community and faculty members within UIHC. Individuals who call the study site will be provided with a brief overview of the purpose and study procedures. Prospective participants may be pre-screened through a telephone survey, if applicable. A copy of the informed consent document will be emailed to the prospective subject for them to review on their own time. If a subject is interested in study participation and passes pre-screening procedures, they will be invited to sign the informed consent document with a study team member (where they will again be provided overview of the study rationale, procedures, risks, and benefits). The individual must make the initiative to call the study center and schedule a meeting to sign the informed consent document. If the prospective participant cannot receive an informed consent document by email, the individual will be invited to review the document with a study team member, but must schedule a separate meeting to sign the document. This ensures that the individual has the chance to review the material in the informed consent on their own time.

It is recognized that the consent process must be carried out in an environment where no coercion is applied and where subjects can be adequately informed of the purpose, nature, procedures, risks and hazards of the study. One of the important features of our screening process is the ability for the prospective participant to leave the study site for review of the informed consent on his/her own time. This additionally demonstrates the reliability of the subject if they schedule a follow-up meeting to sign the informed consent. To assess and document comprehension of the material presented, the study member obtaining consent will complete a consent checklist to verify that the subject understands all aspects of the study including the purpose, procedures, risks and benefits. Checklists are signed by a member of the research team and made part of the permanent record. Prospective subjects will be carefully screened to ensure that they are in excellent physical and mental health. All women of childbearing potential will have a serum pregnancy test performed during screening.

After signing of the informed consent document a screening visit will be scheduled. It is possible for the screening visit to take place on the same day as the informed consent visit if scheduling allows. Screening evaluations will include:

- Questions about demographic information, medical history, and medication history
- Vital signs to determine blood pressure, pulse, temperature, and respiratory rate
- Height and weight
- ECG
- A brief physical exam, performed by the MAI or his designee
- Primary Skin Irritation (PSI) assessment for the site of patch application, completed by a study team member
- Urine drug of abuse screen
- Approximately 40 mL of blood will be collected from an arm or hand vein to test for the following:
  - Hematology parameters including Hgb, Hct, WBC and platelets
  - Chemistry parameters including sodium, potassium, chloride, bicarbonate, BUN, creatinine, AST, ALT
  - Serum pregnancy test (if female of childbearing potential)

Subjects will satisfy all inclusion/exclusion requirements. All screening results will be evaluated against the inclusion/exclusion criteria to confirm subject eligibility (as defined in **section 5.1 and 5.2**). Laboratory results must be within the acceptable ranges in **Appendix B**; abnormal values may be repeated if believed to be a transient and non-clinically significant value. Any clinically significant abnormal laboratory will be shared with the subject and the subject will be advised to follow-up with their physician.

Subjects will be compensated for their time which is calculated as follows:

Screening visit:	\$50
Procedure Day 1:	\$175
Procedure Day 2:	\$75
Procedure Day 3:	\$25
Procedure Day 4:	\$175
Procedure Day 5:	\$175
Procedure Day 6:	\$100
Procedure Day 7:	\$25
Bonus completion of all visits:	\$100
Total compensation:	\$900.00

The money will be mailed directly from Accounts Payable to the subject in the form of a check for a total of \$900.00. This payment schedule is based on the volunteer completing all study procedures. Failure to meet study requirements will result in a prorated payment determined by subject completion. This payment schedule will be followed for subjects in both groups.

## 7.2. Enrollment/Baseline

Total Planned Enrollment: 24 subjects and at least 10 alternates; however, enough alternates will be recruited to ensure 24 subjects complete screening and all seven procedure days. After eligible subjects are enrolled; they will be contacted to return to the CRU on the first procedure day. A washout period of a minimum of 48 hours after conclusion of each study arm will be ensured. Meals and snacks will be provided to the subjects during their stay at the CRU for the first day of each study arm.

### 7.2.1. Prohibitions and Restrictions

Potential subjects must be willing to adhere to the following prohibitions and restrictions during the course of the study to be eligible for participation.

1. Must have a negative urine pregnancy test on Day 1 of each study arm (pregnancy test will be administered only if it has been >30 days since the serum pregnancy test obtained as part of the screening procedures).
2. It is not recommended to consume food or beverages containing alcohol or caffeine for 24 hours prior to each PK sample collection day and until after the last PK sample is collected in each study arm.
3. Subjects should not be under the influence of alcohol, opiates, cocaine, amphetamines, benzodiazepines, hallucinogens, cannabinoids or barbiturates throughout the study. A positive urine drug test will exclude a subject from participating in the study.

4. If a subject has had a recent febrile illness within seven days of scheduled dosing, the start of study drug intake should be postponed until the body temperature is normal for at least 72 hours.
5. Subjects will be advised not to donate blood to a blood bank throughout participation in the study and for at least 60 days after the last procedure day or to participate in an investigational drug study for at least 30 days after completion of the study.
6. Must refrain from sunbathing and tanning for 48 hours prior to beginning of study and throughout the duration of the procedure days.

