**PROTOCOL SUMMARY**

Title:	Absolute Bioavailability/Pharmacokinetic and Residual Drug Analysis of the Lidoderm® System in Healthy Adults
Population:	Healthy, non-smoking adults aged 18-65 years
Number of Sites:	Single site: University of Iowa College of Pharmacy/ University of Iowa Hospitals and Clinics
Study Duration:	Approximately up to 12 months
Subject Participation Duration:	Approximately 3-4 weeks, including the screening period
Description of Study Products:	Lidoderm® patch 5% (Endo Pharmaceuticals Inc.); lidocaine patch 5% (Mylan), lidocaine hydrochloride 20 mg/1 ml preservative free single dose vials (Auromedics Pharma LLC)
Objective:	To determine the rate of lidocaine delivery after using a reference (Lidoderm®) topical drug delivery system in healthy adult volunteers.
Description of Study Design:	
This will be a three arm, open-label, crossover clinical pharmacokinetic study; the three arms will include administration of intravenous (IV) lidocaine hydrochloride, topical administration of a single strength of the reference listed drug (RLD) Lidoderm® 5% topical patch manufactured by Endo Pharmaceuticals, and topical administration of a single strength lidocaine 5% patch manufactured by Mylan.
 
A) Pharmacokinetic Determination of Strength
 
The study will be a three arm, open-label, crossover clinical pharmacokinetic study (n=24 healthy adult subjects, or statistically suitable number) with a minimum 48 hour washout period between each study arm. Each subject will be his/her own control.
 
The study products are:
 
 
• Lidoderm® 5% patch (Endo Pharmaceuticals Inc.)
 
• Lidocaine 5% patch (Mylan)
 
• Lidocaine hydrochloride 20 mg/1 ml preservative free single dose vials (Auromedics Pharma LLC)
 
 
Blood samples will be obtained as follows (based on administration route):

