### 5.1. Subject Inclusion Criteria

Subjects are eligible for this study if they fulfill the inclusion criteria specified below:

1. Men or non-pregnant women, of any ethnic background, between the age of 18 and 65 years old.
2. Provide written informed consent before initiation of any study procedures.
3. Available for follow-up for the planned duration of the study.
4. Able to communicate well with the investigators.
5. Demonstrate comprehension of the protocol procedures and knowledge of study, as demonstrated by a study member filling out a consent checklist form to verify that the subject understands all aspects of the study including the purpose, procedures, risks and benefits.
6. Able to adhere to the study protocol schedule, study restrictions and examination schedule.
7. Subjects must be non-smokers and not regular users of tobacco. They must have refrained from regular and habitual use of nicotine-containing substances, including tobacco products (e.g., cigarettes, cigars, chewing tobacco, gum, patch or electronic cigarettes) over the previous 12 months and must have not used any nicotine-containing products in the previous 30 days.
8. Subjects who are within their ideal body weight (BMI between 18-29.9 kg/m^2).
9. Subjects deemed to be healthy as judged by the Medically Accountable Investigator (MAI), as determined by medical history, physical examination, and medication history.
10. Negative urine drug screening test.
11. Have a normal blood pressure (systolic: 90-139 mmHg; diastolic: 60-89 mmHg) and heart rate (55-100 bpm).
12. Have normal screening laboratories for WBC, Hgb, Hct, platelets, sodium, potassium, chloride, bicarbonate, BUN, creatinine, ALT, AST.
13. Female subjects must be of non-childbearing potential. This is defined as surgically sterile (i.e. history of hysterectomy or tubal ligation), or postmenopausal for more than 1 year (no bleeding for 12 consecutive months). If the person is of childbearing potential they must be non-pregnant at the time of enrollment and on the morning of the first day of each study treatment procedure day (a urine pregnancy test will be administered if it has been >30 days since serum pregnancy test for enrollment). The person must also agree to use hormonal or barrier birth control such as implants, injectables, combined oral contraceptives, some intrauterine devices (IUDs), sexual abstinence, or a vasectomized partner.

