## 5.2. Subject Exclusion Criteria

Subjects will be excluded for any of the following conditions/reasons:

1. Women who are pregnant or lactating or have a positive serum pregnancy test at enrollment or positive urine pregnancy test at any time during the study.
2. Smokers. A “smoker”, for the purposes of the study, will be defined as an individual who has regularly and habitually used nicotine-containing substances, including tobacco products (e.g., cigarettes, cigars, chewing tobacco, gum, patch or electronic cigarettes) over the past 12 months. Occasional recreational use (less than once monthly) will not warrant exclusion unless the individual has used nicotine-containing substances in the previous 30 days before study enrollment.
3. Participation in any ongoing investigational drug trial or clinical drug trial period unless the study is in the follow-up phase and it has been  $\geq$  one month since the subject received any experimental agents or treatments.
4. Abnormal vital signs, defined as:
  - Hypertension (systolic blood pressure  $\geq$ 140 mmHg or diastolic blood pressure  $\geq$ 90 mmHg) at rest on two separate days.
  - Heart rate  $<55$  at rest on two separate days
  - Respiratory rate  $\leq 11$  to  $\geq 18$  breaths per minute
5. Temperature  $>38.0^{\circ}\text{C}$  ( $100.4^{\circ}\text{F}$ ) or symptoms of an acute self-limited illness such as an upper respiratory infection or gastroenteritis within seven days of administration of a study product.
6. History of chronic obstructive pulmonary disease.
7. Positive urine drug screening test.
8. Use of any prescription medication during the period 0 to 30 days or over-the counter medication during the period 0 to 3 days before entry to the study (vitamins, herbal supplements and birth control medications will be allowed).
9. Use of medications or treatments that would significantly influence or exaggerate responses to the test product or that would alter inflammatory or immune response to the product. This includes antihistamines (within 72 hours prior to dosing), systemic or topical corticosteroids within four weeks prior to dosing, use of monoamine oxidase inhibitors 21 days prior to study, cyclosporine, tacrolimus, cytotoxic drugs, immune globulin, Bacillus Calmette-Guerin [BCG], monoclonal antibodies, or radiation therapy.
10. Donation or loss of greater than one pint of blood within 60 days of entry to the study.

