#### Group 1 study schedule

##### 7.3.1. Procedure Day 1: Lidocaine Patch 5% (Mylan)

- Study staff will review any changes in medical history, medication history, and other study qualifications. All inclusion/exclusion criteria must continue to be met.
- Vital signs to determine blood pressure, pulse, temperature, and respiratory rate will be performed within the 60 minutes prior to the application of the three patches.
- Urine pregnancy test will be obtained from women of childbearing potential if it has been more than 30 days since their last pregnancy test; the test must be negative.
- PSI assessment (as explained in **section 9.2.3.**) will be performed prior to patch application.
- The IV catheter will be placed under aseptic technique by an experienced nurse in the CRU.
- Approximately 5 mL of blood will be drawn within the 60 minutes prior to patch application.
- Time 0: Three lidocaine 5% patches (Mylan) will be applied by a member of the study team to the subject's lower back.
  - Each pouch will be numbered with a marker, and the patch corresponding to that pouch and release liner will be numbered the same. The pouches and release liners will be retained.
- Approximately 5 mL of blood will be drawn by an experienced nurse in the CRU at the following time points after patch application:
  - 1:00 hours  $\pm$  5 minutes after patch application (vital signs obtained)
  - 2:00 hours  $\pm$  5 minutes after patch application
  - 3:00 hours  $\pm$  5 minutes after patch application
  - 4:00 hours  $\pm$  5 minutes after patch application (vital signs obtained)
  - 5:00 hours  $\pm$  5 minutes after patch application
  - 6:00 hours  $\pm$  5 minutes after patch application

- 8:00 hours  $\pm$  5 minutes after patch application (vital signs obtained)
- 10:00 hours  $\pm$  5 minutes after patch application
- 12:00 hours  $\pm$  5 minutes after patch application (vital signs obtained, patches removed, and PSI recorded)
- 14:00 hours  $\pm$  5 minutes after patch application (vital signs obtained)
- Adhesion assessment (as explained in **Appendix B**) will be performed at all time points while the subject is wearing the patches.

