### **9.3.2. Reporting of Pregnancy**

Subjects must be of non-childbearing potential, or if of childbearing potential (as determined by the MAI or PI) must be practicing abstinence or using an effective licensed method of birth control (e.g., use hormonal or barrier birth control such as implants, injectables, combined oral contraceptives, some intrauterine devices (IUDs), condoms with spermicidal agents; or have a vasectomized partner). Female subjects will undergo serum pregnancy tests during the Screening Period. Pregnant or lactating women will be excluded from the study. If an eligible female subject has a positive urine pregnancy test on any of the procedure days, she will not be permitted to participate that day and will be discontinued from the study.

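### On the planned 3-4 week course, the 30-day condition means the urine pregnancy test scheduled for each arm is not triggered in any arm

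*Combined protocol and SAP*

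**What the plan says.** Section 7.2.1, item 1, opens with a requirement: "Must have a negative urine pregnancy test on Day 1 of each study arm". Its parenthesis then restricts it: "pregnancy test will be administered only if it has been >30 days since the serum pregnancy test".

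Inclusion criterion 13 (section 5.1) requires a woman of childbearing potential to be "non-pregnant at the time of enrollment and on the morning of the first day of each study treatment procedure day", and follows this with its own parenthesis: "a urine pregnancy test will be administered if it has been >30 days since serum pregnancy test for enrollment". Section 8.1 and footnote 4 of Appendix A also count from the serum test. The first-day visit schedules (7.3.1, 7.3.4, 7.3.5, 7.3.8, 7.3.11, 7.3.12) count differently: "if it has been more than 30 days since their last pregnancy test".

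Section 8.1 places the serum test once, at the screening visit. Appendix A marks a urine test on Days 1, 4 and 5. Several rules act on its result: exclusion criterion 1 covers a "positive urine pregnancy test at any time during the study", section 8.1 stops participation on any positive test, and section 9.3.2 begins "If an eligible female subject has a positive urine pregnancy test on any of the procedure days".

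Three statements set the calendar. The Protocol Summary gives participation as "Approximately 3-4 weeks, including the screening period". Section 7.1 is headed with a screening period of 0 to 30 days. Sections 7.2 and 7.3 set a washout of at least 48 hours between arms and give no maximum.

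**The concern.** The protocol makes absence of pregnancy at the start of each arm a condition of dosing and marks a test for it in all three arms. If the planned course is shorter than the interval that triggers the test, the check exists on the schedule but is not carried out. The only test result behind two patch applications and one intravenous dose would then be the one taken at screening.

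What is at stake is participant and fetal safety in a healthy-volunteer study that section 2.3.2 says brings subjects no direct benefit. A pregnancy beginning after screening would not be found by the scheduled check, and the rules that act on a positive urine result would have no result to act on for that woman.

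**Working it through.** **Inputs**

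- Trigger: more than 30 days since the serum test (5.1, 7.2.1, 8.1, Appendix A).
- Participation: about 3-4 weeks, that is 21-28 days, screening included (Protocol Summary).
- Patch arm: 48 h from application to last sample (7.3.3). Intravenous arm: 10 h (7.3.4).
- Washout: at least 48 h from the last blood draw (7.3.4, 7.3.5).
- Screening window: 0 to 30 days (7.1).

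**Assumptions.** Dosing is in the morning on whole calendar days, the serum test is taken at the start of participation, and the screening window is the interval to Day 1.

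**Step 1: shortest schedule from first application**

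- Arm 1: 0 h to 48 h.
- Arm 2: starts at 48 + 48 = 96 h; last sample at 96 + 10 = 106 h.
- Arm 3: starts at 106 + 48 = 154 h (6.4 days); last sample at 154 + 48 = 202 h (8.4 days).

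With morning dosing, the arms start on calendar days 0, 4 and 7, and the last sample falls on day 9.

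**Step 2: does this fit the stated participation?** Total = screening lag + 9 days. Totals of 21 and 28 days correspond to lags of 12 and 19 days, both inside the 0-30 day window. The 3-4 week figure is therefore reproducible.

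**Step 3: days since the serum test at each dosing.** The gap is the lag plus 0, 4 or 7 days.

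| Total course | Lag | Arm 1 | Arm 2 | Arm 3 | Tests triggered |
|---|---|---|---|---|---|
| 21 days | 12 | 12 | 16 | 19 | 0 of 3 |
| 28 days | 19 | 19 | 23 | 26 | 0 of 3 |

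Longer washouts do not change this. Arm 3 dosing is always at least 2 days before the last sample, so the largest gap in a 28-day course is 28 - 2 = 26 days.

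**Step 4: when is the test triggered?**

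- Arm 3 at minimum washouts: lag + 7 > 30, so a lag of 24 days or more (total 24 + 9 = 33 days, about 4.7 weeks).
- Arm 2 at minimum washouts: lag + 4 > 30, so a lag of 27 days or more (total 36 days or more).
- Arm 1: lag > 30, which the 0-30 day window excludes.
- Whatever the washouts, a test at Arm 3 needs a total of at least 31 + 2 = 33 days.

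| Lag | Arm 1 | Arm 2 | Arm 3 | Triggered at | Total |
|---|---|---|---|---|---|
| 23 | 23 | 27 | 30 | none | 32 |
| 24 | 24 | 28 | 31 | Arm 3 | 33 |
| 27 | 27 | 31 | 34 | Arms 2 and 3 | 36 |
| 30 | 30 | 34 | 37 | Arms 2 and 3 | 39 |

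**Step 5: does the reference test matter?** Not on a 21-28 day course, because until a urine test is done the last test is the serum test. It can matter on a longer one. With a lag of 27 days, a woman is tested at Arm 2. At Arm 3 the serum count is 34 days, so she is tested again, whereas the count from her last test is 34 - 31 = 3 days, so she is not. The Step 4 table uses the serum count.

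**The case against.** The strongest reply is that the 30-day condition is deliberate. It appears in every place that schedules the urine test, including the parenthesis of inclusion criterion 13. A reader might infer from the opening words of that criterion that it demands a test before every dosing. It does not: it demands that the woman not be pregnant and makes the test conditional. Likewise, the opening of section 7.2.1, item 1, is qualified in the same item. Nor do the documents give any figure showing that a 30-day-old result is inadequate. All of this stands.

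A reader might also infer that the trigger can never be reached, so that exclusion criterion 1 and sections 8.1 and 9.3.2 are dead rules. The documents do not support that. The participation figure is approximate, screening may take up to 30 days, and washouts have no upper limit. On longer courses the test is triggered at Arm 3 or Arm 2 and those rules have a result to act on.

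A third tempting inference is that one screening test is all that stands between a pregnant woman and dosing. Sections 5.1 and 9.3.2 also require contraception or abstinence, and eligibility is reviewed at the start of each arm. These safeguards are real, but they concern prevention and review. They do not confirm on the morning of dosing that she is not pregnant.

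What survives the reply is narrower. A check marked for three days is not triggered on the planned course, and its Day 1 instance is not triggered on any course that keeps to the screening window.

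**Conclusion.** The point holds for the planned timeline. On a course of 21-28 days the longest interval from serum test to dosing is 26 days against a trigger above 30, so 0 of 3 scheduled urine tests are done. At minimum washouts this remains so for any screening lag up to 23 days. The Day 1 test cannot be triggered if the 0-30 day window runs to Day 1, which is the natural reading of the section 7.1 heading but is not spelled out there.

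The size is established in days, not in risk. The documents give no number of women of childbearing potential among the 24 subjects, no conception rate and no fetal-risk figure, so no expected number of exposed pregnancies can be derived. The primary pharmacokinetic analysis is not in question. This is a safety check that does not operate as scheduled and costs little to put in order. It should be resolved, but it does not show the trial to be unsafe.

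**What to change.** The sponsor and the investigator should reconcile these places with one another:

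- the 30-day condition in section 5.1 (item 13), section 7.2.1 (item 1), the six first-day schedules in section 7.3, section 8.1 and Appendix A footnote 4;
- the Day 1 requirement that opens section 7.2.1, item 1;
- the participation length in the Protocol Summary;
- the screening window in section 7.1, including a statement of the event it runs to.

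The outcome should be that the check marked on Days 1, 4 and 5 can operate on the course subjects are expected to follow. All of these places should count from the same reference test, serum or last. Which interval applies is for the sponsor and investigator to decide; this review proposes none.

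The cost is amendment wording and, depending on their decision, at most three urine tests per woman of childbearing potential, at visits Appendix A already marks for that test.
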